**Investigator Interests:**

Does the principal investigator, or do any research personnel who are responsible for the design, conduct or reporting of this project or any of their family members (spouse or dependent child) have an incentive or interest, financial or otherwise, that may affect the protection of the human subjects involved in this project, the scientific objectivity of the research or its integrity? Note: The Principal Investigator (Project Director), upon consideration of the individual's role and

degree of independence in carrying out the work, will determine who is responsible for the design, conduct, or reporting of the research.

See Disclosures and Management of Personal Interests in Human Research

<http://www.yale.edu/hrpp/policies/index.html#COI>

Yes • No

Do you or does anyone on the research team who is determined by you to be responsible for the design, conduct or reporting of this research have any patent (sole right to make, use or sell an invention) or copyright (exclusive rights to an original work) interests related to this research protocol?

Yes • No

If yes to either question above, list names of the investigator or responsible person:

*The Yale University Principal Investigator, all Yale University co-investigators, and all Yale University individuals who are responsible for the design, conduct or reporting of research must have a current financial disclosure form on file with the University's Conflict of Interest Office. Yale New Haven Hospital personnel who are listed as co-investigators on a protocol with a Yale University Principal Investigator must also have a current financial disclosure form on file with the University's Conflict of Interest Office. If this has not been done, the individual(s) should follow this link to the COI Office Website to complete the form: <http://www.yale.edu/coi/>*

NOTE: The requirement for maintaining a current disclosure form on file with the University's Conflict of Interest Office extends primarily to Yale University and Yale-New Haven Hospital personnel. **Whether or not they are required to maintain a disclosure form with the University's Conflict of Interest Office, all investigators and individuals deemed otherwise responsible by the PI who are listed on the protocol are required to disclose to the PI any interests that are specific to this protocol.**

## SECTION II: GENERAL INFORMATION

1. **Performing Organizations:** Identify the hospital, in-patient or outpatient facility, school or other agency that will serve as the location of the research. Choose all that apply:

**c. Additional Required Documents (check all that apply):**

- |  |                              |
|--|------------------------------|
|  *YCCI-Scientific and Safety Committee (YCCI-SSC)  |  N/A |
|  *Pediatric Protocol Review Committee (PPRC)   | Approval Date:               |
|  *YCC Protocol Review Committee (YRC-PRC)  | Approval Date:               |
|  *Dept. of Veterans Affairs, West Haven VA HSS   | Approval Date:               |
|  *Radioactive Drug Research Committee (RDRC)   | Approval Date:               |
|  YNHH-Radiation Safety Committee (YNHH-RSC)  | Approval Date:               |
|  Yale University RSC (YU-RSC)  | Approval Date:               |
|  Magnetic Resonance Research Center PRC (MRRC-PRC)   | Approval Date:               |
|  *Nursing Research Committee   | Approval Date:               |
|  YSM/YNHH Cancer Data Repository (CaDR)  | Approval Date:               |
|  Dept. of Lab Medicine request for services or specimens form  |                              |
|  Imaging on YNHH Diagnostic Radiology equipment request form (YDRCTO request) found at http://radiology.yale.edu/research/ClinTrials.aspx |                              |

*\*Approval from these committees is required before final HIC approval is granted. See instructions for documents required for initial submission and approval of the protocol. Allow sufficient time for these requests. Check with the oversight body for their time requirements.*

2. **Probable Duration of Project:** State the expected duration of the project, including all follow-up and data analysis activities. Two years.

3. **Research Type/Phase: (Check all that apply)**

a. **Study Type**

- Single Center Study  
 Multi-Center Study

Does the Yale PI serve as the PI of the multi-site study? Yes  No

- Coordinating Center/Data Management  
 Other:

b. **Study Phase**

- N/A  
 Pilot  Phase I  Phase II  Phase III  Phase IV  
 Other (Specify)

4. **Area of Research: (Check all that apply)** Note that these are overlapping definitions and more than one category may apply to your research protocol. Definitions for the following can be found in the instructions section 4c:

- |   |  |
|---|--|
|  Clinical Research: Patient-Oriented     |  Clinical Research: Outcomes and Health Services |
|  Clinical Research: Epidemiologic and Behavioral    |  Interdisciplinary Research                      |
|  Translational Research #1 (“Bench-to-Bedside”)     |  Community-Based Research                        |
|  Translational Research #2 (“Bedside-to-Community”) |  |

5. Is this study a clinical trial? Yes  No

*NOTE the current ICMJE (International Committee of Medical Journal Editors) definition of a clinical trial: “any research study that prospectively assigns human participants or groups of humans to one or more health-related interventions to evaluate the effects on health outcomes.” Health-related interventions include any intervention used to modify a biomedical or health-related outcome (for example, drugs, surgical procedures, devices, behavioral treatments, dietary interventions, and process-of-care changes). Health outcomes include any biomedical or health-related measures obtained in patients or participants, including pharmacokinetic measures and adverse events”*

If yes, where is it registered?

- Clinical Trials.gov registry   
 Other (Specify)

Registration of clinical trials **at their initiation** is required by the FDA, NIH and by the ICMJE.

*If this study is registered on [clinicaltrials.gov](http://clinicaltrials.gov), there is new language in the consent form and compound authorization that should be used.*

For more information on registering clinical trials, including whether your trial must be registered, see the YCCI webpage, <http://ycci.yale.edu/researchers/ors/registerstudy.aspx> or contact YCCI at [contact])

6. Does the Clinical Trials Agreement (CTA) require compliance with ICH GCP (E6)?  
 Yes  No

7. Will this study have a billable service? *A billable service is defined as any service rendered to a study subject that, if he/she was not on a study, would normally generate a bill from either Yale-New Haven Hospital or Yale Medical Group to the patient or the patient’s insurer. The service may or may not be performed by the research staff on your study, but may be provided by professionals within either Yale-New Haven Hospital or Yale Medical Group (examples include x-rays, MRIs, CT scans, specimens sent to central labs, or specimens sent to pathology). Notes: 1. There is no distinction made whether the service is paid for by the subject or their insurance (Standard of Care) or by the study’s funding mechanism (Research Sponsored). 2. This generally includes new services or orders placed in EPIC for research subjects.*

Yes  No

If answered, “yes”, this study will need to be set up in OnCore, Yale’s clinical research management system, for Epic to appropriately route research related charges. Please contact [[contact]](mailto:[contact])

8.. Are there any procedures involved in this protocol that will be performed at YNHH or one of its affiliated entities? Yes \_\_\_ No X *If Yes, please answer questions a through c and note instructions below. If No, proceed to Section III.*

a. Does your YNHH privilege delineation currently include the **specific procedure** that you will perform?

b. Will you be using any new equipment or equipment that you have not used in the past for this procedure?

c. Will a novel approach using existing equipment be applied?

If you answered “no” to question 8a, or "yes" to question 8b or c, please contact the YNHH Department of Physician Services ([name]) for prior approval before commencing with your research protocol.

*Please note that if this protocol includes Yale-New Haven Hospital patients, including patients at the HRU, the Principal Investigator and any co-investigators who are physicians or mid-level practitioners (includes PAs, APRNs, psychologists and speech pathologists) who may have direct patient contact with patients on YNHH premises must have medical staff appointment and appropriate clinical privileges at YNHH. If you are uncertain whether the study personnel meet the criteria, please telephone the Physician Services Department at [contact]. **By signing this protocol as a PI, you attest that you and any co-investigator who may have patient contact has a medical staff appointment and appropriate clinical privileges at YNHH.***

**SECTION III: FUNDING, RESEARCH TEAM AND TRAINING**

1. **Funding Source:** Indicate all of the funding source(s) for this study. Check all boxes that apply. Provide information regarding the external funding source. This information should include identification of the agency/sponsor, the funding mechanism (grant or contract), and whether the award is pending or has been awarded. Provide the M/C# and Agency name (if grant-funded). If the funding source associated with a protocol is “pending” at the time of the protocol submission to the HIC (as is the case for most NIH submissions), the PI should note “Pending” in the appropriate section of the protocol application, provide the M/C# and Agency name (if grant-funded) and further note that University (departmental) funds support the research (until such time that an award is made).

PI	Title of Grant	Name of Funding Source	Funding	Funding Mechanism
[name] MS	Sublingual Riluzole for the Social Anxiety Disorder	Biohaven Pharmaceuticals	 Federal  State  Non Profit  Industry  Other For Profit  Other	 Grant-M#  Contract#  Contract Pending  Investigator/Department Initiated  Sponsor Initiated Other, Specify:

			 Federal  State  Non Profit  Industry  Other For Profit  Other	 Grant-M#  Contract#  Contract Pending  Investigator/Department Initiated  Sponsor Initiated Other, Specify:
			 Federal  State  Non Profit  Industry  Other For Profit  Other	 Grant-M#  Contract#  Contract Pending  Investigator/Department Initiated  Sponsor Initiated Other, Specify:

IRB Review fees are charged for projects funded by Industry or Other For-Profit Sponsors. Provide the Name and Address of the Sponsor Representative to whom the invoice should be sent. **Note: the PI's home department will be billed if this information is not provided.**

## SECTION V: RESEARCH PLAN

1. **Statement of Purpose:** State the scientific aim(s) of the study, or the hypotheses to be tested. The goal of the current proposal is to examine the acute anxiolytic effects of BHV-0223 on subjects with social anxiety disorder performing an anxiety-provoking speech task.
  
2. **Background:** Describe the background information that led to the plan for this project. Provide references to support the expectation of obtaining useful scientific data.
  - Social Anxiety Disorder is common and causes significant impairment.
  - First-line treatments for Social Anxiety Disorder are only partially effective. Many SAD patients experience little or inadequate symptom relief with available treatments.
  - Riluzole is a glutamate modulating agent that would potentially target a new mechanism to treat anxiety.
  - Riluzole has been shown to reduce anxiety in adults Major Depression, Generalized Anxiety Disorder and Obsessive Compulsive Disorder.

Social anxiety disorder (SAD) affects approximately 12.1% of all Americans and is defined as a “marked and persistent fear of one or more social situations,” causing impairment and distress (1). SAD typically impairs academic achievement, work productivity, social relationships, and results in a significantly poorer quality of life(2). SAD is associated with subsequent development of depression, alcoholism, and cardiovascular disease (1-3).

Roughly one-third to one-half of patients with generalized SAD do not experience significant clinical benefit from current evidence-based treatments, such as pharmacotherapy with selective serotonin reuptake inhibitors (SSRI) or venlafaxine and cognitive behavioral therapy (CBT) (4-7). Failure of anxiety relief in patients with SAD is a source of substantial morbidity, distress, and decreases in quality of life.

Several pharmacological treatments are utilized on an as-needed basis because of their short-term, potent anti-anxiolytic effects. These pharmacological agents include benzodiazepines (which target the gamma-aminobutyric acid-A receptor (GABA-A) and beta-blockers (beta adrenergic receptor antagonists) (8, 9). Although, benzodiazepines are quite effective at reducing anxiety over the short term (10) in specific situations (e.g. flying on an airplane), their side-effects and tolerability currently limit their usefulness in many situations (e.g. performance or public-speaking anxiety) (8, 9). Benzodiazepine use is associated with impaired short-term concentration, decreased alertness and psychomotor impairment (9, 11). Chronic benzodiazepine use is further associated with physiologic dependence, rebound anxiety on discontinuation and, possibly even interference with the efficacy of CBT (one of the first-line treatments for anxiety) (9, 11). Beta-blockers, on the other hand, are effective at acutely reducing the peripheral physical symptoms of anxiety (e.g. heart palpitations, tremors etc.) but have no effect on

the cognitive or emotional symptoms of anxiety (9, 10, 12-15). Novel pharmacological treatments are needed to improve patient outcomes with SAD, both chronically to reduce symptoms and acutely to reduce impairment during situations where symptoms are most likely to be impairing (e.g. public speaking or performance anxiety).

Riluzole is a glutamate-modulating agent that is FDA-approved for the treatment of amyotrophic lateral sclerosis. Riluzole has been documented at physiologically realistic drug concentrations to (1) inhibit certain voltage-gated sodium channels reducing glutamate release and (2) enhance astrocytic uptake of extracellular glutamate. Several uncontrolled trials have suggested the efficacy of riluzole for reducing anxiety symptoms in adults with Generalized Anxiety Disorder, Obsessive-Compulsive Disorder and Major Depression (16-20). An 8-week, open-label, fixed-dose, trial of 18 adults with GAD given riluzole (100mg/day) demonstrated a significant improvement over time with riluzole treatment (17). Sixty-seven percent of adults with GAD responded to riluzole treatment (defined as a greater than 50% decrease in HAM-A) and 44% of subjects had a remission of anxiety symptoms after riluzole treatment (HAM-A<8) (17). No double-blind, placebo-controlled trials of riluzole have been conducted in the treatment of patients with primary anxiety disorders. Riluzole is quite well tolerated in psychiatric and ALS population, with nausea and sedation being the most common side effects. Elevation of liver function tests is a common occurrence with chronic riluzole administration and necessitates periodic monitoring but has been without clinical consequences in psychiatric trials with riluzole to date.

Biohaven Pharmaceuticals recently developed BHV-0223, which is a sublingual form of riluzole, being investigated for the treatment of ALS. BHV-0223 has several advantages over the currently available riluzole formulation in that it (1) avoids first-pass metabolism, thereby reducing overall drug burden to the liver and (2) has produced subjective reports of relaxing effects when administered to healthy subjects.

3. **Research Plan:** Summarize the study design and research procedures using non-technical language that can be readily understood by someone outside the discipline. **Be sure to distinguish between standard of care vs. research procedures when applicable, and include any flowcharts of visits specifying their individual times and lengths.** Describe the setting in which the research will take place.

- We are proposing a crossover trial in which 20 adults with Social Anxiety Disorder with the primary outcome being anxiety on the impromptu speech task.
- Each subject will be given BHV-0223 (or placebo) under double-blind conditions 1-hour before performing the impromptu speech task on 2 separate study days.
- There will be a 2 to 10 day washout period between study days.
- There will be a final Follow-up visit 2 to 10 days later to do blood work and complete physical exam.

Overview:

We propose conducting a double-blind, placebo controlled crossover study examining the effects of BHV-0223 on public speaking anxiety. Twenty subjects with DSM-5 defined social anxiety disorder and clinically significant public speaking anxiety on the Impromptu Speech Task will be enrolled in a challenge study. Subjects will be given BHV-0223 (or placebo) under double-blind crossover conditions 1 hour prior to performing each of 2 impromptu speech tasks. The two study days involving BHV-0223 (or placebo) administration and impromptu speech task will be separated by 2 to 10 days to allow for medication washout. There will be a final follow-up visit 2 to 10 days later to perform a complete Physical exam and do follow-up liver function testing and a Complete Blood Count. Our primary outcome will examine BHV-0223's effects (compared to placebo) on self-rated anxiety during the impromptu speech task. We will also collect physiological measures of anxiety, clinician-rated measures of anxiety, and measures of speech performance as secondary outcomes.

Screening:

A baseline screening assessment to determine study eligibility, clinical ratings, and physical health will be conducted at least one week prior to the challenge study.

*Medical Assessments*

During the screening visit, vital signs (BP, HR: supine, standing X 2-3 min), physical exam (including a comprehensive exam of the oral cavity see Appendix 1), and clinical laboratory tests (i.e. CBC with differential, complete metabolic panel (CMP) (including electrolytes, LFTs, BUN, creatinine and glucose), TFTs, urine drug screen, and routine urinalysis) will be completed. A pregnancy test will be given to all females of childbearing age enrolled in the study prior to participating in the study sessions. We will also perform a visual inspection of the mouth cavity to assess local tolerability before and 1 hour after administering study medication on each study day (please see appendix document for further details).

*Psychiatric Assessments*

The SCID (Structured Clinical Interview for DSM disorders) on the screening day to verify presence of social anxiety disorder and the absence of other psychiatric conditions (psychotic disorders, current substance abuse/dependence etc.). The *Liebowitz Social Anxiety Scale (LSAS)* will be administered to determine that public speaking anxiety symptoms are significant enough for inclusion in the trial. The LSAS is a rating scale that assesses SAD severity (21) and a 5-item subscale rates public speaking fear (22). Psychiatric rating scales examining the severity of anxiety (*Hamilton Anxiety Rating Scale (HAM-A)* (23)) and depressive symptoms *Hamilton Depression Rating Scale (HAM-D)* (24) will also be administered. Per FDA guidelines, suicidal ideation and behavior will be monitored using the C-SSRS(25) at screening and on every visit day.

Intervention:

Subjects will be given BHV-0223 35mg or placebo in a random order as assigned through the CMHC pharmacy with a 2 to 10 day separation between task days. Randomization will be performed by the CMHC pharmacy. The identity of the treatments will be concealed by the use of study drugs that are identical in packaging, labeling, schedule of administration and appearance. Placebo and study drug will be prepared in a like fashion in the CMHC pharmacy. Unblinding of a specific patient's randomization assignment will only occur during the study in the case of specific patient emergencies.

BHV-0223 is a sublingual, oral-disintegrating tablet containing 35mg of riluzole drug substance. BHV-0223 35mg tablets have shown bioequivalence to riluzole 50mg administered orally (please see PIND 128411 for further details). The half-life of BHV-0223 is just under 8 hours. Riluzole is a member of the benzothiazole class of medications. Chemically, its molecular formula is  $C_8H_5F_3N_2OS$  and its molecular weight is 234.2. The efficacy of riluzole in the treatment of ALS was established in two well-controlled studies. Patients randomized to treatment with riluzole showed longer time to tracheotomy or death compared to those treated with placebo. The recommended dose of riluzole in the treatment of ALS is 50mg taken every 12 hours (at least an hour before, or two hours after, a meal to avoid food-related decreases in bioavailability). Riluzole's mechanism of action in the treatment of ALS is unknown but thought to be due to its down-modulation of glutamatergic neurotransmission.

The most commonly observed adverse reactions of riluzole, dosed at 100mg/day, in placebo-controlled trials were asthenia (19.2%), nausea (16.3%), dizziness (3.9%), decreased lung function (10.2%), diarrhea (2.9%), abdominal pain (5.1%), pneumonia, vomiting (4.2%), vertigo (1.9%), oral paresthesia, anorexia (3.2%), and somnolence (1.9%). In a study with approximately 4,000 patients given riluzole for ALS, three cases of neutropenia were reported within the first two months of treatment.

Rarely, jaundice is a side effect as well. Riluzole has also been found to cause elevations in serum aminotransferase even in patients without a history of liver disease. Experience with riluzole in 800 patients with ALS demonstrated that approximately 50% of riluzole treated patients experienced at least one ALT/SGPT level above the upper limit of normal, 8% had elevations >3x upper limit of normal (ULN), and 2% >5x ULN. BHV-0223 may have reduced overall drug burden on the liver as the sublingual formulation avoids first-pass metabolism.

Subjects will be asked to come back 2 to 10 days after the second task day to perform a complete Physical Exam, Visual examination of the oral cavity, Vital signs (BP, HR: supine, standing X 2-3 min), Complete Blood count and Liver function test.

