### Assessments

#### *Impromptu Speech Behavioral Assessment Test*

The impromptu speech BAT will be performed 1 hour after the subject receives study medication as outlined in the table below (26-28). Participants will be asked to speak about pre-determined topics for 10 minutes to a small audience of research staff

(27). Patients with more severe social anxiety symptoms are often not able to speak for the full 10 minutes and have shorter speech lengths when compared to those with less severe social anxiety symptoms (26-28). VAS-anxiety, State-Trait Anxiety Inventory and the Self-Statement during Speech Test (SSPS) (28) will be assessed before and after the speech. The Local Tolerability Assessment (Appendix 1) will be performed at screening, baseline, 1 hour after receiving the study medication and before discharge.

The Table below shows the assessment schedule for participants enrolling in the trial.

Measure	Screening	Challenge DAY 1					2-10 day washout period	Challenge DAY 2					2-10 days	Follow up visit
		Baseline	0	1h	2h	3h		Baseline	0	1h	2h	3h		
Local Tolerability Assessment	X	X		X		X		X		X		X		
Impromptu Speech Task				X					X					
VAS-anxiety	X	X	X	X	X	X		X	X	X	X	X		
VAS-speech performance				X					X					
SSPS		X		X				X	X					
STAI		X		X				X	X					
DSST		X		X				X	X					
Immediate and Delayed Word Recall		X		X				X	X					
Clinical-rated VAS-anxiety				X					X					
Clinician rated VAS-speech performance				X					X					
LSAS	X	X						X						
SCID	X													
C-SSRS	X					X						X		
Physical Exam with Vital signs (BP, HR: supine, standing X 2-3 min) and Visual exam of the oral cavity	X	X				X		X				X		X
Blood test	X													X
Urine Test	X	X						X						
EKG	X													
STUDY MEDICATION ADMINISTRATION			X						X					

The rating scales utilized in the trial are detailed in the table below. Ratings will be conducted by raters that are blinded to treatment assignment and will not be present during medication administration.

- RATING SCALES:**
- 1) *Visual Analog Scale (VAS) of Anxiety States:* The VAS includes scales for anxiety, drowsiness, high, irritability, anger, and sadness. These scales are 100 mm lines marked by participants at a point corresponding to the apparent intensity of the feeling state (0=none, to 100=most ever) (29). We will also use clinician-rated visual analogue scales to measure subject anxiety and speech performance during the Impromptu Speech Task.

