  - 2) *Self-Statement During Public Speaking Scale (SSPS):* The SSPS is a rating scale used to measure cognitions that occurred during a speech (28).
  - 3) *State-Trait Anxiety Inventory (STAI):* The STAI is a standardized rating scale of trait and state anxiety (30).
  - 4) *Digit Symbol Substitution Task (DSST):* Digit Symbol Substitution Tasks requires the subject to match symbols with their corresponding digit. It consists of 9 digit symbols matched with their corresponding numerical digit. Subjects are asked to match as many number-symbol pairs within a 90 second time limit. Performance

of the DSST has been demonstrated to be impaired by acute treatment with benzodiazepines (31).

- 5) Immediate and Delayed Word Recall Test – In this task, a list of 10 words will be repeated 3 times to subjects at a pace of 1 word every 2 seconds. Immediately after presentation of the list and 5 minutes later subjects will be asked to recite as many of the words as they can from memory. Performance on this task has been demonstrated to be impaired by acute treatment with benzodiazepines (31).
- 6) Local Tolerability Assessment: Systematized oral cavity inspection checklist (Appendix 1).
- 7) Columbia-Suicide Severity Rating Scale (C-SSRS) – Assessment of suicidal ideation and behavior in clinical and research settings(25)

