### **Worsening of symptoms**

Since Riluzole or placebo is added to the patients' current medications, the risk of symptoms worsening in this study is not significantly greater in this clinical trial than it would be if the patient's medications were changed as part of standard clinical care. Furthermore, the acute effects of study medications should dissipate within 8 hours of taking the single dose of medication. The only additional risks in this study are potential adverse effects of riluzole.

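### The C-SSRS is scheduled on challenge days only at 3 h, after the dose and the speech, with no same-day pre-dose rating, and the follow-up visit has none despite the text

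*Combined protocol and SAP*

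**What the plan says.** Section V, item 3 (Research Plan, Psychiatric Assessments) states that "suicidal ideation and behavior will be monitored using the C-SSRS(25) at screening and on every visit day". It gives no time of day.

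The only timed schedule is the table under Assessments, introduced by "The Table below shows the assessment schedule for participants enrolling in the trial". Its C-SSRS row is marked at Screening, Day 1 3h and Day 2 3h. The Baseline and 0 cells are empty on both days, and so is the follow-up visit.

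On the order of events within a day: "The impromptu speech BAT will be performed 1 hour after the subject receives study medication as outlined in the table below". On the intervals between ratings, the screening assessment "will be conducted at least one week prior to the challenge study", and the two challenge days "will be separated by 2 to 10 days to allow for medication washout".

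The rating-scale list describes what the C-SSRS measures but gives neither a version nor a recall period. Under the Moderate Risk DSMP, Attribution of Adverse Events, the principal investigator grades each event on a five-level scale from definite to unrelated.

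**The concern.** A rating at 3 h is useful for detecting suicidality after study drug, but it needs something to be compared with. Here the last rating before the first dose is at least a week old, and the last rating before the second dose was made 2 to 10 days earlier, just after the other treatment.

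Two things are at stake. The first is safety: a subject who has developed suicidal ideation since the last rating would take the study drug and give a speech that the protocol itself expects to raise anxiety before the scheduled instrument is used. The second is interpretation: when a 3 h rating is positive, the record contains no pre-dose value from that day to show whether the finding was already present. Side-effects are a listed secondary measure and are also reviewed at the look after 10 subjects. In a 20-subject crossover, a single event assigned to the wrong treatment would be noticeable.

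Separately, the text and the table disagree about the follow-up visit.

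**Working it through.** The plan gives no figure on this point to reproduce. The check is a reading of the table, followed by the lengths of the intervals between ratings.

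**Step 1: the table.** The rows have 15 cells, including the measure name. Mapping them to the column headings gives:

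| Row | Marks |
|---|---|
| Study medication | Day 1 at 0; Day 2 at 0 |
| C-SSRS | Screening; Day 1 3h; Day 2 3h |
| Physical exam and vital signs | Screening; Baseline and 3h on both days; Follow-up |
| Local tolerability | Screening; Baseline, 1h and 3h on both days |
| LSAS | Screening; Baseline on both days |

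Some Day 2 marks look displaced by one column (the speech sits at 0 instead of 1h). The C-SSRS marks line up with the 3h marks of the physical exam and local tolerability rows on both days, and a shift of one column would not turn a 3h mark into a pre-dose one. Table damage does not explain the gap.

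**Step 2: other places that might fill it.** The HAM-D is described only with the screening assessments and has no table row. The inclusion and exclusion criteria contain no suicidality item. Section X, item 4 says that participants will be asked systematically about adverse events and symptom severity, but gives no time and does not name suicidality. No pre-dose suicidality check on a challenge day is scheduled anywhere.

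**Step 3: length of the unrated interval before each dose.** Inputs are the minimum of 7 days from screening to Day 1, the 2 to 10 days between challenge days, and the rating at 3 h. Dosing is assumed to be at the same clock time on both days.

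- Day 1: at least 7 × 24 = 168 h before the dose, then 3 h after it (at least 171 h from rating to rating).
- Day 2: rating to rating is 2 × 24 = 48 h to 10 × 24 = 240 h. The part before the Day 2 dose is 48 − 3 = 45 h to 240 − 3 = 237 h.

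The recall period decides what happens to those hours. If the 3 h rating looks back to the previous rating, it mixes them with the 3 h after the dose. If it looks back only to dosing, they are never rated.

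**Step 4: the hours after 3 h.** The protocol says that "the acute effects of study medications should dissipate within 8 hours of taking the single dose of medication". Hours 3 to 8 (8 − 3 = 5 h) after the Day 1 dose can therefore be captured only by a rating made after the Day 2 treatment. The same hours after the Day 2 dose have no later C-SSRS, because the follow-up cell is empty.

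**Step 5: follow-up visit.** The text in Psychiatric Assessments covers every visit day. The table marks a physical exam and a blood test at follow-up but no C-SSRS, and the description of that visit under Intervention does not list one either. These places must be reconciled.

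**The case against.** **The table does meet the text on challenge days.** There is one rating on each, and the text sets no time. This stands: on those days the problem is a design choice and not a contradiction. The contradiction is at the follow-up visit. Whether the guidelines that the text invokes require a pre-dose rating cannot be checked from the documents.

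**A reader might infer that events will be filed against the wrong treatment.** The documents do not support this as a certainty. It needs a recall period that is not stated and a rule that the visit day fixes attribution. Attribution is in fact made case by case, with a review of all adverse events as each subject completes, and nothing prevents onset from being recorded. What remains is that this judgment has no same-day pre-dose rating to draw on.

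**A reader might turn the hours into shares of events.** Since 3/48 = 6.3% and 3/240 = 1.3%, it is tempting to say that 94% to 99% of positive Day 2 ratings began before the dose. Those are shares of clock time. The documents give no event rate and no timing of onset, so they say nothing about shares of events.

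**Ideation on the day after Day 1, recorded on Day 2, might be read as a hidden drug effect.** By the protocol's own 8-hour expectation, that lies outside the acute effect. Only about 5 h of the 45 to 237 h before the Day 2 dose could conceal one.

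**The C-SSRS is not alone in lacking a challenge-day baseline.** Blood tests are repeated at Screening and Follow-up with no challenge-day value. The argument rests on the C-SSRS being rated after the dose without a reference, not on its being unique.

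**Subjects are seen before dosing.** Baseline includes a physical exam, the LSAS and visual analogue scales that cover sadness and irritability; a study doctor monitors the challenge and a psychiatrist is available. This reduces the practical risk but does not amount to a suicidality rating.

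**A Baseline rating does not by itself prevent dosing.** This also stands. What follows from a positive rating is a clinical rule, and none is proposed here.

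**Conclusion.** The point holds, within limits. On both challenge days the C-SSRS comes only after the dose and the speech, so anything that has arisen in the preceding interval (at least 168 h before Day 1, 45 to 237 h before Day 2) is first formally rated after that day's exposure. The 3 h rating has no same-day reference, which weakens the information available for attribution. Confusion between treatments is a possible consequence and not an established one. The follow-up visit is a plain inconsistency between text and table.

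The gap applies to every subject, but expected events among 20 subjects are few. The cost lies in safety and attribution, not in power. The conclusion rests on the table as read, and on no pre-dose suicidality check being scheduled elsewhere in the document. It should be fixed because the change is small.

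**What to change.** - Add a C-SSRS mark in the Baseline (pre-dose) column of both challenge days, covering the time since the previous rating.
- State that the 3 h rating covers the time since dosing.
- Record the onset time of any finding. Count as new on that day's treatment only ideation or behaviour that is new or worse than at that day's Baseline. Report Day 2 Baseline findings by onset date and leave their attribution to the investigator.
- Reconcile the Psychiatric Assessments text with the schedule table, and with the description of the follow-up visit, on whether the C-SSRS is done at follow-up. If it is, the period after the Day 2 3 h rating is also covered.

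Cost: 2 × 20 = 40 short interviews at most, done when the Baseline exam and LSAS are already taking place, plus at most 20 if the follow-up rating is added (60 in all). No extra visits or subjects are needed. The downside is a few more minutes of subject time before dosing.
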